2. OBJECTIVES AND ENDPOINTS

This study will evaluate the safety, efficacy, pharmacokinetics, and immunogenicity of induction treatment consisting of obinutuzumab in combination with atezolizumab plus polatuzumab vedotin (G+Atezo+Pola) in patients with relapsed or refractory FL and rituximab in combination with atezolizumab + polatuzumab vedotin (R+Atezo+Pola) in patients with relapsed or refractory DLBCL, followed by post-induction treatment with G+Atezo (referred to as maintenance) in patients with FL who achieve a CR, a PR, or stable disease at EOI and post-induction treatment with R+Atezo (referred to as consolidation) in patients with DLBCL who achieve a CR or PR at EOI (see Section 3.1 for details). Specific objectives and corresponding endpoints for the study are outlined below, in accordance to study changes from Protocol BO29561, Version 7.

In this study, "study treatment" refers to the combination of all study treatment components.

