3.1.3.1 Treatment Regimens and Safety Run-In Rules

Patients with DLBCL enrolled in the safety run-in phase and the expansion phase were planned to receive induction treatment with R + Atezo + Pola for a total of 6 cycles.

Patients achieving a CR or PR at EOI were eligible to receive consolidation treatment with R + Atezo.

[figure not shown]
As of 1 March 2018, patients with RR DLBCL will continue to be treated as outlined in [Table 4](#). As of Protocol BO29561, Version 7, patients who have completed or prematurely discontinued induction treatment will proceed to the safety follow-up without consolidation treatment.

Table 4 Induction Treatment for Patients with Diffuse Large B-cell Lymphoma

Cycle	R + Atezo + Pola (21-Day Cycles) Treatment Group
1–6	Rituximab 375 mg/m ² IV on Day 1 Polatuzumab vedotin 1.8 mg/kg IV on Day 1

IV=intravenous.

Figure 1 Study Schema

C=cycle; CR=complete response; D=day; D1C6=Day 1 of Cycle 6; EOI=end of induction; FL=follicular lymphoma; G=obinutuzumab; M=month; Pola=polatuzumab vedotin; PR=partial response; R=rituximab; q2m=every 2 months; SD=stable disease.

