3.3.2 Rationale for Dose and Schedule

3.3.2.1 Rationale for Obinutuzumab and Rituximab Dose and Schedule

For patients with FL, the dose and schedule of obinutuzumab in the induction regimen will be 1000 mg IV on Days 1, 8, and 15 of Cycle 1 and Day 1 of each subsequent 21-day cycle (Cycles 2–6). This is based on the recommended dose and schedule of obinutuzumab in the ongoing Phase III program in patients with NHL. For this protocol, patients will be treated for 6 cycles during the induction phase. The dose and schedule of obinutuzumab in the maintenance regimen (FL) will be 1000 mg IV administered every 2 months for up to 2 years. This dosing administration is based on the obinutuzumab maintenance regimen that was administered in the Phase III GAO4753g study (Sehn et al. 2015).

For patients with DLBCL, the dose and schedule of rituximab in the induction regimen will be 375 mg/m² on Day 1 of each 21-day cycle (Cycles 1–6). This is based on the recommended dose and schedule for rituximab in this setting (see Rituximab Investigator's Brochure and NCCN Guidelines® 2016). For this protocol, patients will be treated for 6 cycles during the induction phase. The dose and schedule of rituximab in the consolidation regimen (DLBCL) was 375 mg/m² IV administered every 2 months for up to 8 months. The consolidation regimen was modeled after the FL maintenance therapy. The rationale for treatment duration is presented in Section 3.3.2.4.

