Patients with relapsed or refractory DLBCL who are not suitable for or do not benefit from consolidative autologous transplantation exhibit a poor prognosis. Responses obtained with different rituximab treatment regimens tested in clinical trials (e.g., rituximab in combination with bendamustine, with gemcitabine plus oxaliplatin, or with lenalidomide) are of short duration, with the longest reported median PFS of approximately 7 months observed in one study of rituximab plus bendamustine (Ohmachi et al. 2013). Thus, 8 months of consolidation treatment with R+Atezo, for total treatment duration of approximately 12 months, aimed at prolonging the anti-tumor immune response, and was considered to be a reasonable exploratory therapeutic approach with an anticipated positive benefit-risk ratio. On the basis of the complementary mechanism of action between rituximab and atezolizumab, and considering the aggressiveness of refractory or relapsed DLBCL, the study was designed to investigate the safety and efficacy of this doublet in the consolidation setting. As of Protocol BO29561, Version 7, atezolizumab treatment is discontinued, and hence, consolidation treatment is removed. Patients with RR DLBCL will be treated only through the induction phase with rituximab and polatuzumab vedotin.

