4.3.2.4 Rituximab

Rituximab will be administered by IV infusion at the dose of 375 mg/m² on Day 1 of Cycles 1–6 during induction treatment and on Day 1 of every other month (i.e., every 2 months) during consolidation treatment.

Body surface area (BSA) will be determined at screening and should be used to calculate the dose of rituximab throughout the study unless the patient's weight increases or decreases by >10% from screening, in which case BSA should be recalculated and used for subsequent dosing. In obese patients (defined as body mass index $\geq 30 \text{ kg/m}^2$), there is no BSA cap and actual body weight, not adjusted weight, is recommended. Empiric dose adjustment for obese patients may be implemented per institutional guidelines.

The infusion of rituximab may be split over two days if the patient is at increased risk for an IRR (high tumor burden or high peripheral lymphocyte count). Administration of rituximab may be continued on the following day, if needed, for patients who experience an adverse event during the rituximab infusion.

If a dose of rituximab is split over two days, both infusions must occur with appropriate premedication (see Section 4.3.2.7) and at the first infusion rate (see [Table 5](#)).

Rituximab infusions will be administered according to the instructions in [Table 5](#). If a patient tolerates the first three cycles of study treatment without significant infusion reactions, rituximab may be administered as a rapid infusion in accordance with local institutional guidelines.

During the treatment period, rituximab must be administered to patients in a setting where full emergency resuscitation facilities are immediately available. Patients should be under close supervision of the investigator at all times.

Rituximab should be administered as a slow IV infusion through a dedicated line. After the end of the first infusion, the IV line or central venous catheter should remain in place for ≥ 2 hours in order to administer IV drugs, if necessary. If no adverse events occur after 2 hours, the IV line may be removed or the central venous catheter may be de-accessed. For subsequent infusions, the IV line or central venous catheter should remain in place for at least 1 hour after the end of the infusion. If no adverse events occur after 1 hour, the IV line may be removed or the central venous catheter may be de-accessed.

Table 5 Administration of First and Subsequent Infusions of Rituximab

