4.3.2.6 Post-Induction Treatment

Patients with FL who achieve a CR, a PR, or stable disease at EOI will receive maintenance treatment with obinutuzumab for 24 months, as outlined in [Table 8](#).

Maintenance treatment should start 8 weeks (\pm 1 week) after Day 1 of Cycle 6 and will continue until disease progression or unacceptable toxicity for up to 24 months.

Table 8 Maintenance Treatment for Patients with Follicular Lymphoma

Treatment	Dose	Route	Regimen (Months 1–24)
Obinutuzumab	1000 mg	IV	Day 1 of every other month (i.e., every 2 months), starting with Month 1

FL=follicular lymphoma; IV=intravenous.

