5.1.7.3 Toxities during Maintenance Treatment

Table 15 provides guidelines for management of toxicities that occur during maintenance treatment.

Table 15 Guidelines for Management of Toxicities that Occur during Maintenance Treatment

Event	Action To Be Taken
Hematologic toxicity: Grade 3 or 4	
Withhold obinutuzumab/rituximab.Administer G-CSF for neutropenia per institutional guidelines.Administer RBCs or platelets as required.If there is improvement to Grade ≤ 2, resume obinutuzumab at full dose.If obinutuzumab is withheld for >42 days due to adverse event, permanently discontinue obinutuzumab/rituximab.
Non-hematologic toxicity: Grade ≥ 2	
For atezolizumab-related toxicities with possible immune etiology¹:
 
Follow guidelines presented in Table 14 for the management of atezolizumab-related toxicities with possible immune etiology (i.e., autoimmune colitis, hepatitis, pancreatitis, hypothyroidism, hyperthyroidism, pneumopathy, skin toxicity, or ocular toxicity). 
For non-immune mediated toxicities:
 
Withhold study treatment.If there is improvement to Grade ≤ 1 or baseline, resume obinutuzumab/rituximab at full dose.If study treatment is withheld for >42 days due to adverse event, permanently discontinue study treatment.

G-CSF=granulocyte colony-stimulating factor.

¹ Please refer to atezolizumab Investigators Brochure for additional information.

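### The rituximab dosing section still provides consolidation for DLBCL that other sections removed: 0 versus up to 4 post-induction infusions, to be reconciled

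*Combined protocol and SAP*

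**What the plan says.** **Text that still carries consolidation**

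- Section 4.3.2.4 sets rituximab at 375 mg/m² for six cycles, and its schedule reads "during induction treatment and on Day 1 of every other month (i.e., every 2 months) during consolidation treatment". It has no date and no reference to Version 7.
- Section 2 describes "post-induction treatment with R+Atezo (referred to as consolidation) in patients with DLBCL who achieve a CR or PR at EOI" and says that its objectives follow the Version 7 changes. Section 2.2.2 and the synopsis also present the efficacy of R + Atezo consolidation as something to be evaluated.
- Table 15 in Section 5.1.7.3, which Section 5.1.7 names as the post-induction guidance, tells sites for non-immune toxicity to "resume obinutuzumab/rituximab at full dose".

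**Text that removes it**

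- Section 3.1.3.1, as of Version 7: "patients who have completed or prematurely discontinued induction treatment will proceed to the safety follow-up without consolidation treatment". Section 4.2 says the same, dated from 1 March 2018.
- Section 3.3.2.4: "consolidation treatment is removed", with DLBCL treatment confined to induction.
- Section 4.3.2.6 and Tables 6 to 8 contain no DLBCL regimen after induction.
- Appendix 2 places rituximab in Cycles 1 to 6 only. After the end-of-induction (EOI) visit it has a 90-day safety visit and survival follow-up, but no treatment visit.

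**Text that describes the former schedule:** Section 3.3.2.1, in the past tense: "The dose and schedule of rituximab in the consolidation regimen (DLBCL) was 375 mg/m² IV administered every 2 months for up to 8 months".

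**The concern.** For a DLBCL patient in complete or partial response at EOI, the rituximab dosing section and the design sections give instructions that cannot both be followed. Neighbouring text was updated: the atezolizumab dosing section (4.3.2.2) and the rituximab consolidation sentence in Section 3.3.2.1 were put into the past tense. The clause in Section 4.3.2.4 was not, and that is where a site looks for how to give rituximab.

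Two things would be at stake if a site acted on that clause. Study drug would be given with no treatment visit in Appendix 2. The last dose of study treatment would also move later, and three things follow from it: the 90-day adverse event window (Section 5.3.1), the end of study, which waits for the 90-day visits (Section 3.2), and the main safety analysis, which runs to end of study (Section 6.5). Section 6.5 does not separate events that follow post-induction rituximab. In addition, the secondary objective presents as current a treatment phase that the same protocol has closed.

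**Working it through.** **1. Reproduce the plan's own figure.** Section 3.3.2.4 gives a total DLBCL treatment duration of about 12 months when 8 months of consolidation are included.

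- Induction: 6 cycles × 21 days = 126 days; 126 / 30.4375 = 4.1 months.
- With calendar months: 4.1 + 8 = 12.1 months.
- With 28-day months (the convention in the footnote to Table 2): (126 + 8 × 28) / 30.4375 = 11.5 months.
- With consolidation starting 8 weeks after Day 1 of Cycle 6, as for maintenance in follicular lymphoma: (105 + 56 + 224) / 30.4375 = 12.6 months, or 13.3 with calendar months.

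All are near 12 months, so the 8-month length is consistent with the stated total.

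**2. Count the infusions.** Section 3.3.2.1 says "The consolidation regimen was modeled after the FL maintenance therapy". Table 8 gives that maintenance on "Day 1 of every other month (i.e., every 2 months), starting with Month 1". Applied to Months 1–8, the infusion months are 1, 3, 5 and 7, which is 4 infusions. Counting 0, 2, 4, 6 and 8 would give 5, but with a Month 1 start the fifth would fall in Month 9, outside the 8 months.

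**3. Compare the two readings for one DLBCL responder.**

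| Text followed | Post-induction infusions | Total infusions | Cumulative dose |
|---|---|---|---|
| Sections 3.1.3.1, 3.3.2.4, 4.2 | 0 | 6 | 6 × 375 = 2250 mg/m² |
| Section 4.3.2.4 with the length in Section 3.3.2.1 | up to 4 | up to 10 | 10 × 375 = 3750 mg/m² |

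The difference is up to 4 / 6 = 67% more infusions.

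**4. Effect on the safety window.** The documents give no start date for DLBCL consolidation. Assuming the follicular lymphoma rule (8 weeks after Day 1 of Cycle 6) and 28-day months, Day 1 of Month 7 falls 56 + 6 × 28 = 224 days after Day 1 of Cycle 6. The 90-day window would then close at day 224 + 90 = 314 instead of day 90. This illustrates the longest shift for one patient; it is not an estimate of what happened.

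**5. What each analysis admits.** Section 6.6 runs efficacy on data as of 1 March 2018 plus the assessment window. Section 6.5 runs the main safety analysis to end of study and adds a sensitivity analysis on data as of 1 March 2018 plus 90 days. Rituximab given after that date is therefore largely outside the efficacy data but inside the main safety analysis.

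**The case against.** The strongest reply is that this is one uncorrected clause. The removal is explicit, dated and stated in three sections, and the regimen tables agree with it. Section 4.3.2.4 alone gives no start, length or eligibility for consolidation, so it cannot be carried out from that section; the 8-month length survives only as history. Future tense proves little, since the protocol also uses it for completed enrollment. Section 3.1.4 says patients no longer receive polatuzumab vedotin, a drug scheduled for all six induction cycles, which implies that induction is over. This stands as to weight: the clause looks like carry-over, and few or no patients would reach the disputed decision under Version 8. It does not remove the contradiction in the dosing section.

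Four stronger readings are tempting and are not supported.

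- *The objectives and Table 15 also authorise rituximab consolidation.* The objectives describe R + Atezo, and atezolizumab is stopped in all patients, so they cannot authorise rituximab alone. Table 15 is a maintenance table that never names DLBCL or consolidation, and its hematologic row resumes obinutuzumab only.
- *Best response and overall survival would be contaminated.* The censoring in Section 6.6 largely prevents this. Overall survival is exploratory, and its objective in Section 2.2.3 names only G + Atezo + Pola.
- *Some 5 to 12 of the 23 DLBCL patients are affected.* That applies response rates of 20% and 54% from Section 1.5.4.3 to everyone enrolled (23 × 0.20 = 4.6; 23 × 0.54 = 12.4). The first rate is for obinutuzumab plus polatuzumab vedotin; the second is at 2.4 mg/kg, above this trial's 1.8 mg/kg maximum. Neither says who could still reach the decision after 1 March 2018.
- *Appendix 2 has no visits after EOI.* It keeps the 90-day and survival follow-up columns; only treatment visits are absent.

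**Conclusion.** The inconsistency holds and should be corrected. Section 4.3.2.4 conflicts with Sections 3.1.3.1, 3.3.2.4 and 4.2, and with the content of Section 4.3.2.6 and Appendix 2, on whether DLBCL patients receive rituximab after induction. Its size per patient is 0 against up to 4 infusions. That count assumes the 8-month length in Section 3.3.2.1 and a Month 1 start borrowed from follicular lymphoma maintenance. Table 15 and the objectives are secondary: leftover wording that should agree with whatever rule is stated.

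The documents do not give the number of patients affected. It is probably small, on the reading of Section 3.1.4 that induction has ended, though they do not exclude a post-EOI infusion since 1 March 2018. No effect on the primary endpoint or sample size is shown. The analysis question that remains concerns the main safety analysis and the 90-day reporting window. This review does not say which treatment rule is right.

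**What to change.** - Reconcile Section 4.3.2.4, Table 15, Sections 2 and 2.2.2 and the synopsis with Sections 3.1.3.1, 3.3.2.4, 4.2 and 4.3.2.6 and Appendix 2, so that one post-induction rule for DLBCL appears throughout.
- Have the objectives state that R + Atezo consolidation data come only from patients treated before 1 March 2018. Do not delete them: Section 3.3.2.4 says DLBCL patients previously received this treatment, and best response during the study can include it.
- List any DLBCL patient given study rituximab after EOI since 1 March 2018, and identify those doses in the main safety analysis so that events following them can be seen.

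The cost is wording in one amendment, one listing and one flag in the safety outputs. No procedures or visits are added.

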4.3.2.6 Post-Induction Treatment

Patients with FL who achieve a CR, a PR, or stable disease at EOI will receive maintenance treatment with obinutuzumab for 24 months, as outlined in [Table 8](#).

Maintenance treatment should start 8 weeks (\pm 1 week) after Day 1 of Cycle 6 and will continue until disease progression or unacceptable toxicity for up to 24 months.

Table 8 Maintenance Treatment for Patients with Follicular Lymphoma

Treatment	Dose	Route	Regimen (Months 1–24)
Obinutuzumab	1000 mg	IV	Day 1 of every other month (i.e., every 2 months), starting with Month 1

FL=follicular lymphoma; IV=intravenous.

4.3.2.7 Premedication and Other Prophylaxis Treatment

Patients should receive premedication as outlined in [Table 9](#) below.

Table 9 Premedication

Timepoint	Patients Requiring Premedication	Premedication	Administration
Cycle 1, Day 1	• All patients	• Oral corticosteroid ^a	Administer at least 1 hour prior to obinutuzumab or rituximab infusion
	• All patients	• Antihistamine drug ^b • Oral analgesic/anti-pyretic ^c	Administer at least 30 minutes prior to obinutuzumab or rituximab infusion
	• Patients at risk for TLS (e.g., because of bulky disease or renal impairment (creatinine clearance < 70 mL/min)	• Allopurinol or suitable alternative such as rasburicase, along with adequate hydration	Administer prior to obinutuzumab or rituximab infusion
Cycle 1, Days 8 and 15	• Patients with no IRR during the previous infusion	• Oral analgesic/anti-pyretic ^c	Administer at least 30 minutes prior to obinutuzumab infusion. For patients receiving rituximab premedication may be omitted at the investigator's discretion.
Cycles 2 and beyond, Day 1	• Patients with Grade 1 or 2 IRR during the previous infusion	• Antihistamine drug ^b • Oral analgesic/anti-pyretic ^c	Administer at least 30 minutes prior to obinutuzumab infusion
	• Patients with Grade 3 IRR, wheezing, urticaria, or other symptoms of anaphylaxis during the previous infusion	• Oral corticosteroid ^a	Administer at least 1 hour prior to obinutuzumab or rituximab infusion
	• Patients with bulky disease	• Antihistamine drug ^b • Oral analgesic/anti-pyretic ^c	Administer at least 30 minutes prior to obinutuzumab infusion
	• Patients still at risk for TLS	• Allopurinol or suitable alternative such as rasburicase, along with adequate hydration	Administer prior to obinutuzumab or rituximab infusion

IRR = infusion-related reaction; TLS = tumor lysis syndrome.

^a Treat with 100 mg of prednisone or prednisolone, 20 mg of dexamethasone, or 80 mg of methylprednisolone. Hydrocortisone should not be used because it has not been effective in reducing rates of IRR.

^b For example, 50 mg of diphenhydramine.

^c For example, 1000 mg of acetaminophen/paracetamol.

4.3.3 Investigational Medicinal Product Accountability

All IMPs required for completion of this study (obinutuzumab, rituximab, and polatuzumab vedotin) will be provided by the Sponsor. The study site will acknowledge receipt of IMPs using the IxRS to confirm the shipment condition and content. Any damaged shipments will be replaced.

An IMP will either be disposed of at the study site according to the study site's institutional standard operating procedure or returned to the Sponsor with the appropriate documentation. The site's method of IMP destruction must be agreed to by the Sponsor. The site must obtain written authorization from the Sponsor before any IMP is destroyed, and IMP destruction must be documented on the appropriate form.

Accurate records of all IMPs received at, dispensed from, returned to, and disposed of by the study site should be recorded on the Drug Inventory Log.

4.3.4 Post-Trial Access to, Obinutuzumab, Rituximab, and Polatuzumab Vedotin

Patients may continue to receive study treatment and undergo scheduled assessments as part of an extension study. Currently, the Sponsor does not have any plans to provide post-trial access to any IMP or interventions to patients who do not qualify for the extension study. The Roche Global Policy on Continued Access to Investigational Medicinal Product is available at the following Web site:

http://www.roche.com/policy_continued_access_to_investigational_medicines.pdf

4.4 CONCOMITANT THERAPY

Concomitant therapy includes any medication (e.g., prescription drugs, over-the-counter drugs, herbal or homeopathic remedies, nutritional supplements) used by a patient from 7 days prior to the screening period to the visit at EOI or at the end of post-induction treatment, whichever occurs later. All such medications should be reported to the investigator and recorded on the Concomitant Medications eCRF.

4.4.1 Permitted Therapy

Premedication should be administered as described in Section [4.3.2.7](#).

Patients who use oral contraceptives, hormone replacement therapy, or other maintenance therapy should continue their use.

Patients using concomitant medication that could possibly worsen thrombocytopenia-related events (e.g., platelet inhibitors and anticoagulants) may be at a greater risk of bleeding. When possible, replace prior vitamin K antagonist therapy with low-molecular-weight heparin (LMWH) prior to Day 1 of Cycle 1.

Hematopoietic growth factors are allowed if clinically indicated and used in accordance with the prescribing information. Granulocyte colony-stimulating factor (G-CSF) may be administered in each cycle of therapy as primary prophylaxis for neutropenia, per American Society of Clinical Oncology, EORTC, and European Society for Medical Oncology guidelines or per each site's institutional standards.

Prophylactic treatment with antibiotics should be administered as per standard practice.

The patients who receive strong CYP3A4 inhibitors or P-glycoprotein (P-gp) inhibitors in combination with polatuzumab vedotin will be closely monitored for any adverse reactions.

Necessary supportive measures for optimal medical care will be given throughout the study according to institutional standards.

